6.2.3 Follow-up Visits

- Accelerometer (3 months): Within 1 week of participants hitting 3 months (13 weeks) a CSA accelerometer will be mailed to their home for them to wear for 1 week and mail back.
- Visit 2 (6 months): Visit 2 will occur within 2 weeks of participant hitting 6 months (26 weeks) of the intervention and will include.
 - Medication review
 - MVPA using accelerometer
 - Cognitive Function
 - Cardiovascular Fitness
 - Quality of Life Questionnaire
 - Anthropometrics
 - Physical Function (Sub-sample).
 - Caregiver Outcomes (Sub-sample).
 - MRI (Sub-sample).
 - Adverse Events Review
- Accelerometer (9 months): Within 1 week of participants hitting 9 months (39 weeks) a CSA accelerometer will be mailed to their home for them to wear for 1 week and mail back.

6.2.4 At-Home Data Collection

- Attendance
 - Session attendance for both group MVPA and individual education/support sessions from baseline to 12 mos. will be obtained from records maintained by the health educator, and expressed as the percent of possible sessions. Attendance at group MVPA sessions will be defined as being logged in to the video conference and remaining on the screen for the entire 30-min session. Attendance at individual support/education sessions, for the both exercise and UC conditions, will be defined as answering the Zoom call, and being present on screen for the entire session.
- Fitbit
 - Daily MVPA will be tracked from the Fitbit device. It will be used by the Health Coaches to provide feedback.
- Exercise Video Recordings:
 - Use of recorded exercise sessions (RL and RH only) will be tracked using Dropbox which provides information on how many times each user watched a video
- Adverse Events
 - As described below, we will ask participants for any adverse events at group exercise sessions and individual education sessions.

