3 STUDY DESIGN

This is a 12-mo. randomized control trial in 80 non-demented adults with DS. Participants will be randomized (2:2:1) to attend 40 min. remotely delivered group MVPA sessions (Zoom™ Video Conferencing Inc., San Jose, CA) at a low frequency (1 session/wk., RL) or high frequency (3 sessions/wk., RH), or a usual care control (UC). In addition to the group MVPA sessions, participants in both the RL and RH arms will receive a step counter (Charge 3™, Fitbit, San Francisco, CA), access to resources for increasing MVPA, and one 20-min remotely delivered (Zoom™) individual support/education session/wk. Content for both the RL and RH arms will be identical with the exception of group MVPA session frequency (1 vs. 3/wk.). Participants in the UC arm will receive a step counter (Charge 3™, Fitbit, San Francisco, CA), access to resources for increasing MVPA, and monthly remote (Zoom™) individual support/education. The primary outcomes, daily MVPA will be assessed by portable accelerometer (ActiGraph wGT3XBT, ActiGraph LLC, Pensacola, FL) at baseline, 3, 6, 9 and 12 mos. The secondary outcomes, cardiovascular fitness, quality of life, cognitive function and brain parameters related to AD (whole and regional brain volume, functional connectivity, cerebral blood flow) will be assessed at baseline, 6, and 12 mos. With the exception of assessment of daily MVPA by accelerometer, all outcomes will be assessed at the University of Kansas Medical Center, in Kansas City, KS. The exercise intervention will take place in the participants home.

| Table 1: Design Overview | | | |
|--|-------------------------------|------------------------------|------------------------------|
| | Intervention Arms | | |
| | Remote High (n=32) | Remote Low (n=32) | Usual Care (n=16) |
| MVPA recommendation | 150 min/wk. | 150 min/wk. | 150 min/wk. |
| Group MVPA sessions | Yes | Yes | No |
| Delivery format | Zoom™ video conferencing | Zoom™ video conferencing | NA |
| Frequency | 3d/wk. | 1d/wk. | NA |
| Intensity | ≥ 3 METS | ≥ 3 METS | NA |
| Duration | 40 min | 40 min | NA |
| Content | Stretch/aerobic activity/RE | Stretch/aerobic activity/RE | NA |
| Access to PA resources | Yes | Yes | Yes |
| MVPA Self-monitoring | Fitbit | Fitbit | Fitbit |
| Education/support/feedback sessions | Yes | Yes | Yes |
| Participants | DS adult + Study Partner | DS adult + Study Partner | DS adult + Study Partner |
| Frequency | 2x/mo | 2x/mo | 2x/mo |
| Delivery format | Zoom™ | Zoom™ | Zoom™ |

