Orientation. Each participant and their study partner will be asked to attend a group orientation session (~60 min.) conducted at the University of Kansas Medical center and led by their health educator. In addition to describing study requirements and distributing iPads, Fitbits, resistance bands, etc., this meeting is designed to establish rapport between the health educator and participants, and between participants themselves, prior to initiating the group video conference sessions. The health educator will describe and demonstrate the ZoomTM software and the Fitbit and will allow time for practice and questions. Additionally, basic stretching exercises, the use of the resistance bands, and simple dance movements will be demonstrated and practiced.

Group sessions-schedule. Group exercise sessions will be scheduled between 10 a.m. and 7 p.m., 3 days/wk. for RH and 1 day/wk. for RL. This time window was selected based on the preference of participants in our 12-wk pilot trial in individuals with DS. Prompts reminding participants of upcoming sessions will be sent via the iPad. The same health educator will conduct MVPA sessions for both the RH and RL groups in each cohort to minimize health educator effects.

Group sessions-Delivery. All MVPA sessions will be conducted by a health educator experienced in working with individuals with DS and supervised by [name]. Group sessions will be delivered using an iPad tablet computer provided to all participants. The iPad will be pre-loaded with video-conferencing software (ZoomTM) which allows participation by multiple users. Participants will be provided with an iPad/HDMI adaptor, which allows video conference sessions to be displayed on a larger TV screen, if desired. Tutorials describing trouble shooting for common technical problems, e.g., internet connectivity etc., will be loaded on the iPad. Participants with technical issues during the intervention can also contact research staff by phone or email. Access to non-study related materials, e.g., web browsing, app store, etc., will be blocked on all iPads. The iPads for both groups will also be pre-loaded with the Fitbit application.

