Homework assignments. The group exercise sessions have the potential to provide 30 min./wk. of MVPA for the RL group and 90 min./wk. for the RH group. Thus, MVPA outside these sessions will be required to meet the 150 min weekly recommendations. Health educators will provide weekly challenges in the form of meeting a goal for increased steps, trying a new activity, or creating and performing their own exercise routine etc. Participants will be provided access to video recordings of all group sessions that can be followed on their own to help in meeting weekly MVPA goals across the 12 mo. trial, if desired. Recordings will be sent to Dropbox and will be accessible to participants on the iPad. We will also provide information regarding increasing physical activity, available from the National Center on Health, Physical Activity and Disability (NCHPAD) and the Special Olympic athletes home training guide. Participants will be asked to document MVPA outside group sessions using the Fitbit, rather than video recordings as used in our pilot due to poor compliance with the video recording protocol. Participants press a button on the Fitbit at the beginning and end of each MVPA session to differentiate planned MVPA from other daily activity. Activity monitoring using the Fitbit is being successfully implemented to monitor the MVPA component in our on-going trial of weight management in adults with IDD (DK114121, [name], MPI).

Education/support sessions. Bi-Weekly (2x/mo) 20-min. education/support sessions will be delivered to participants and their study partners remotely on the iPad using Zoom™. These sessions, led by the health educator, will be designed to educate and support the participant with meeting their 150 min./wk. MVPA goal. Each session will include a review of MVPA self-monitoring data, goal setting, strategies to increase and support MVPA, and discussion of a topic relevant to MVPA including: the importance of MVPA for health and function, how to include MVPA in the daily schedule, reducing barriers to MVPA, appropriate types of activity, creating a safe environment for MVPA, alternative activities for inclement weather, importance of hydration, etc. Session outlines and materials will be preloaded on the iPad where they can be accessed by participants at any time.

UC Intervention.

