Orientation. Participants and their study partner will be asked to attend an orientation session (~60 min.) conducted at the University of Kansas Medical center and led by their health educator. In addition to describing study requirements and distributing iPads, Fitbits, resistance bands, etc., this meeting is designed to establish rapport between the health educator and participants. The health educator will describe and demonstrate the Zoom™ software and the Fitbit and will allow time for practice and questions. Additionally, basic stretching exercises and the use of the resistance bands will be demonstrated and practiced.

Intervention. The UC intervention will follow the traditional approach to promote increased MVPA in individuals with DS previously used by our group ⁴⁻⁶ and others ⁷⁻⁹. Participants will receive an iPad tablet loaded with information regarding increasing MVPA available from NCHPAD and the Special Olympic athletes home training guide, and will also receive resistance bands and a Fitbit for self-monitoring MVPA (described below). Bi-weekly 20-min. education/support sessions, identical to the education/support sessions provided in the RL and RH arms, described above, will be

delivered to participants and their study partners remotely on the iPad using Zoom^M. Session outlines and materials will be preloaded on the iPad where they can be accessed by the participant at any time.

MVPA-self monitoring. Participants in all 3 groups will be asked to wear a Fitbit Charge 3TM (35.5 mm x 28 mm) activity tracker on their non-dominant wrist over the duration of the 12-mo. trial. This request may appear onerous; however, wearing the Fitbit is akin to wearing a wristwatch. Real-time data from the Fitbit is automatically transferred, via the web, to cloud storage (Fitabase, Small Steps Labs LLC, San Diego, CA), thus participant burden is minimal. Immediate participant feedback via a graphic display of daily steps, minutes of sedentary time, time spent in light, moderate and vigorous PA will be available on the iPad. This data, accessible to health educators, will be used to provide motivation and feedback during the education/support sessions. Participants will be reminded to wear and charge the Fitbit during the individual support/education sessions, and will receive automatic reminder messages via the iPad using the iCal app. These procedures were used successfully in our previous trials in adults with DS^{4, 6, 10, 11}.

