burden (physical, emotional, financial). Caregiver stress will be assessed using the Caregiver Self-Assessment Questionnaire (CSAQ), which is a caregiving-specific measure of psychosocial stress and is an appropriate measure for depression screening⁷⁷. Caregiver quality of life will be assessed using the Adult Carer Quality of Life Questionnaire (AC-QoL)⁷⁸, which covers eight different domains for caregivers: support for caring; caring choice; caring stress; money matters; personal growth; sense of value; ability to care; and caregiver satisfaction.

Feasibility. Retention. Retention will be measured as the percentage of participants who complete the 12 mo. intervention, defined as completing the 12 mo. outcome assessments. Session attendance. Session attendance for both group MVPA and individual education/support sessions from baseline to 12 mos. will be obtained from records maintained by the health educator, and expressed as the percent of possible sessions. Attendance at group MVPA sessions will be defined as being logged in to the video conference and remaining on the screen for the entire 30-min session. Attendance at individual support/education sessions, for the both exercise and UC conditions, will be defined as answering the Zoom call, and being present on screen for the entire session. Use of recorded exercise sessions (RL and RH only) will be tracked using Dropbox which provides information on how many times each user watched a video. Safety. Safety will be measured by number of participants reporting a serious adverse event, i.e., any untoward medical occurrence that results in death, is life-threatening, requires inpatient hospitalization or results in persistent or significant disability/incapacity.

Descriptive outcomes. To characterize our study sample, we will measure weight, height and waist circumference in participants at baseline, 6, and 12 mos. Weight will be measured in light clothing on a calibrated scale (Model #PS6600, Belfour, Saukville, WI) to the nearest 0.1 kg. Standing height will be measured with a portable stadiometer (Model #IP0955, Invicta Plastics Limited, Leicester, UK). BMI will be calculated as weight (kg)/height (m²). Waist circumference will be assessed using the procedures described by Lohman et al.⁷⁹.

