6.2.5 Completion/Final Evaluation

- *Visit 3 (12 months):* Visit 3 will occur within 2 weeks of participant hitting 12 months (52 weeks) of the intervention and will include.
 - Medication review
 - MVPA using accelerometer
 - Cognitive Function
 - Cardiovascular Fitness
 - Quality of Life Questionnaire
 - Anthropometrics
 - Physical Function (Sub-sample).
 - Caregiver Outcomes (Sub-sample).
 - MRI (Sub-sample).
 - Adverse Events Review
 - Interview

7 **SAFETY ASSESSMENTS**

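### Adverse-event enquiry follows session contacts, so Remote High is asked about 6.4 to 7.5 times as often as Usual Care; serious events are little affected, but brief non-serious events would be under-counted in Usual Care

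*Combined protocol and SAP*

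**What the plan says.** On enquiry, Section 6.2.4 says "we will ask participants for any adverse events at group exercise sessions and individual education sessions". Section 7.2 has staff watch for events at outcome assessments, exercise sessions and education sessions. Section 7.4 collects reports made at those same three kinds of contact, and Section 7.5 follows events up at the next session of either kind.

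On contact frequency, Section 5 schedules group sessions "3 days/wk. for RH and 1 day/wk. for RL"; Usual Care (UC) has none. For the two exercise arms, Remote High (RH) and Remote Low (RL), it says "Bi-Weekly (2x/mo) 20-min. education/support sessions will be delivered to participants and their study partners remotely". For UC it says "Bi-weekly 20-min. education/support sessions, identical to the education/support sessions provided in the RL and RH arms". Table 1 gives twice a month in all three arms, and the Précis text agrees in substance. The text of Section 3 differs: one "individual support/education session/wk" for RH and RL, and "monthly remote (Zoom™) individual support/education" for UC. It also disagrees with the copy of Table 1 printed in the same section.

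On the outcome, Section 5 (Feasibility) says "Safety will be measured by number of participants reporting a serious adverse event", meaning death, threat to life, hospital admission or lasting disability. Section 8.3 plans to estimate proportions, with precision stated for each arm, and gives no between-arm safety contrast.

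On visits, Sections 6.2.2, 6.2.3 and 6.2.5 each list "Adverse Events Review", at baseline, Month 6 and Month 12. The schedule table in Section 6.1 marks adverse events at baseline and Month 6, and under Weekly, Bi-Monthly and Daily, but not at Month 12.

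**The concern.** How often an event is asked about depends on the randomised arm. An event that has passed and been forgotten before the next contact is lost, and the wait for that contact is about two days in RH and about two weeks in UC. More events in RH could then reflect more asking, not more harm.

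This bears on Secondary Aim 2, which includes the safety of all three arms. The harms Section 7.1 expects are strains, sprains and soreness, which are minor and usually brief. Section 7.3 counts events whether or not they are related to the research, so ordinary passing illness is also picked up more readily in RH and RL. Section 7.4 sends adverse events, not only serious ones, to the DSMB periodically. Once data are collected without a record of where each event was first reported, the effect of asking cannot be separated from the effect of exercise.

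**Working it through.** **The plan's own figures.** The documents state no number or ratio of enquiries. The only figures attached to the safety analysis are the Section 8.3 margins of 0.09 (n=32) and 0.125 (n=16). They reproduce as one standard error at p = 0.5: √(0.25/32) = 0.088 and √(0.25/16) = 0.125. The 95% half-widths would be 1.96 times these, 0.173 and 0.245. That is a separate matter. What counts here is that the margins are given arm by arm and not for a difference.

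**Step 1: scheduled enquiries over 52 weeks.** Group sessions: RH 3 × 52 = 156, RL 1 × 52 = 52, UC 0. Support sessions: 2 × 12 = 24 in each arm, or 26 if held every two weeks. Clinic reviews common to all arms: 2 after baseline, or 3 with baseline.

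| Counting rule | RH | RL | UC | RH/UC |
|---|---|---|---|---|
| 24 support, at home only | 180 | 76 | 24 | 7.5 |
| 26 support, at home only | 182 | 78 | 26 | 7.0 |
| 24 support + 2 visits | 182 | 78 | 26 | 7.0 |
| 24 support + 3 visits | 183 | 79 | 27 | 6.8 |
| 26 support + 2 visits | 184 | 80 | 28 | 6.6 |
| 26 support + 3 visits | 185 | 81 | 29 | 6.4 |
| Section 3 text (52 v 12), at home only | 208 | 104 | 12 | 17.3 |

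On the first row RL/UC is 76/24 = 3.2. Adding 2 or 3 visits to the Section 3 row gives 210/14 = 15.0 or 211/15 = 14.1.

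**Step 2: attendance.** These counts assume full attendance. If group attendance is 50% to 90% (assumption) and support attendance is full, RH/UC runs from (78 + 24)/24 = 4.25 to (140.4 + 24)/24 = 6.85.

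**Step 3: what unequal asking does to the counts.** The mean gap between enquiries is 365/180 = 2.0 days in RH, 365/76 = 4.8 in RL and 365/24 = 15.2 in UC. As an illustration, assume an event is captured only if an enquiry falls within w days of it. Capture is then min(1, w/gap). Take the gap as 15.2 days in UC, 7 in RL (weekly group session) and at most about 3 in RH (three sessions spread over the week). With equal true rates:

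| Recall w (assumed) | UC | RL | RH | Apparent RH/UC |
|---|---|---|---|---|
| 3 days | 0.20 | 0.43 | 1.00 | 5.1 |
| 7 days | 0.46 | 1.00 | 1.00 | 2.2 |
| 14 days | 0.92 | 1.00 | 1.00 | 1.09 |
| 15.2 days or more | 1.00 | 1.00 | 1.00 | 1.0 |

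**Step 4: does anything else equalise the enquiry?** The Weekly and Daily marks in the Section 6.1 table carry no arm restriction. But no weekly or daily adverse-event enquiry is described for UC, and under the twice-monthly schedule the only weekly contact is the group session, which UC lacks.

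**The case against.** A reader might infer that the trial's planned safety comparison is biased against the exercise arms, by something like the 7.5-fold difference in contacts. The documents do not support that, for four reasons.

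- Section 8.3 estimates proportions and specifies no safety test, contrast or rate ratio.
- The outcome is participants with a serious event. A hospital admission is unlikely to be forgotten within 15 days, study partners are asked to attend every support session, and every arm has reviews at Months 6 and 12. On the model above, any event recalled for 15.2 days or more gives a ratio of 1.0.
- The contact ratio is not a bias factor. Capture cannot exceed 100%, so extra asking beyond the recall window adds nothing.
- Section 7.3 does not count normal exercise symptoms such as fatigue or light soreness as adverse events, which removes many of the complaints most sensitive to frequent asking.

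All of this stands, and it limits the point to non-serious events. It is also fair that Section 7.4 does not say the DSMB reports are split by arm, and that the missing Month 12 mark is clerical, since Section 6.2.5 lists the review.

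What does not stand is the suggestion that other reporting routes even things out. Section 7.4 accepts reports from staff and others, but again at testing visits, group sessions and education sessions. Strains, sprains and passing illness are not excluded by Section 7.3. Estimates for three arms set side by side will be compared, whether or not a test is planned.

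**Conclusion.** The point holds for non-serious, short-lived adverse events. Ascertainment is unequal by design: 180, 76 and 24 scheduled at-home enquiries, with RH/UC between 6.4 and 7.5 under the twice-monthly support schedule. The text of Section 3 would put it at 17.3, and that conflict must be reconciled.

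The direction is clear: RH and RL would appear to have more such events than UC. The size is not known. It rests on an assumed recall period and full attendance, with an apparent RH/UC ratio of about 2.2 at 7 days, 1.09 at 14 days and none beyond about 15 days. The planned serious-event outcome is little affected. This should be corrected because it is cheap and cannot be repaired afterwards, but it does not undermine the main safety measure.

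**What to change.** - At every support session and at the Month 6 and Month 12 visits, ask the same structured question in all arms. It should cover the whole period since the last such contact, whether or not the event was already mentioned at a group session.
- Add a source-of-report field that allows more than one source, since one event may surface at both kinds of session.
- Keep counting serious events from every source in every arm. Restricting them to the common contacts would drop a serious event disclosed only at a group session. Only RH and RL could lose events that way, so the imbalance would be reversed.
- Present non-serious events by arm from the common contacts, with all-source counts alongside and events found only at group sessions listed separately.
- Reconcile support-session frequency between the text of Section 3, Table 1, the Précis and Section 5. The common contacts must fall at the same interval in every arm for this to work.
- Mark the Month 12 adverse-event review in the Section 6.1 table to match Section 6.2.5.

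The cost is one form field, a paragraph of analysis wording and some repeated questioning in RH and RL. The common-contact table may omit some minor RH and RL events, but these stay fully listed and reported. Earlier prompting at group sessions may still help recall in those arms, so some imbalance could remain. Ongoing monitoring and expedited reporting are unchanged.

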6.2.5 Completion/Final Evaluation

- *Visit 3 (12 months):* Visit 3 will occur within 2 weeks of participant hitting 12 months (52 weeks) of the intervention and will include.
 - Medication review
 - MVPA using accelerometer
 - Cognitive Function
 - Cardiovascular Fitness
 - Quality of Life Questionnaire
 - Anthropometrics
 - Physical Function (Sub-sample).
 - Caregiver Outcomes (Sub-sample).
 - MRI (Sub-sample).
 - Adverse Events Review
 - Interview

7 **SAFETY ASSESSMENTS**

